⁶Anastrozole is continued until the day of surgery. If premenopausal continue goserelin 3.6 mg SC monthly throughout the neoadjuvant duration. PD0332991 is also continued until the day of surgery in patients who started cycle 5 therapy.

⁷ See Postoperative Therapy and Follow-up Schema

*NCI9170: A phase II trial of neoadjuvant MK-2206 in combination with anastrozole for PIK3CA mutant clinical stage 2 or 3 ER+ and HER2- breast cancer

[†]If the NCI9170 trial is not open or was open but is now closed at the participating institution

POSTOPERATIVE THERAPY AND FOLLOW-UP SCHEMA

Except those who refuse for followup or did not undergo surgery

* Follow-up for patients who do not receive adjuvant PD 0332991 will take place annually for 5 years post-surgery or until recurrence (whichever comes first). Follow-up for patients who do receive adjuvant PD 0332991 will be tied to treatment, not to date of surgery. These patients will be followed for a total of 5 years (inclusive of the up to 2 years of adjuvant PD 0332991 treatment), with follow-up after discontinuation of PD 0332991 taking place annually after the last dose or until recurrence (whichever comes first). Patients who discontinue adjuvant PD 0332991 early (do not complete the full 23 cycles of treatment) will be followed annually following the last dose of PD 0332991 to get as close as possible to 5 years of post-surgery follow-up or until recurrence (whichever comes first).

¹ Endocrine therapy that is not Anastrozole can be used if patient cannot tolerate Anastrozole (See Section 5.3)

Glossary of Abbreviations

AE	Adverse event
ALT (SGPT)	Alanine transaminase (serum glutamate pyruvic transaminase)
ANC	Absolute neutrophil count
AST (SGOT)	Aspartate transaminase (serum glutamic oxaloacetic transaminase)
AUC	Area under the curve
BCS	Breast conserving surgery
B-HCG	Beta human chorionic gonadotropin
BUN	Blood urea nitrogen
CBC	Complete blood count
Cdk	Cyclin dependent kinase
CFR	Code of Federal Regulations
CNS	Central nervous system
CR	Complete response
CRF	Case report form
CT	Computed tomography
CTCAE	Common Terminology Criteria for Adverse Events
CTEP	Cancer Therapy Evaluation Program
DCIS	Ductal carcinoma in situ
DNA	deoxyribonucleic acid
DOB	Date of birth
DSM	Data and Safety Monitoring
DSMC	Data Safety Monitoring Committee
ECG (or EKG)	Electrocardiogram
ECOG	Eastern Cooperative Oncology Group
EDTA	ethylenediaminetetraacetic acid
ER	Estrogen receptor
FDA	Food and Drug Administration

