in the PIK3CA WT cohort and all 15 (100%, 90% CI: 82-100%) patients in the PIK3CA mutant cohort. The study met its primary endpoint of achieving a CCCA rate of 66% in C1D15. In addition, 26 patients who did not achieve CCCA with anastrozole alone on C1D1 achieved complete CCCA in C1D15 post 2 weeks of combination therapy. These data justify the evaluation of PD 0332991 in the adjuvant setting. The international PALLAS (PALbociclib CoLlaborative Adjuvant Study) trial is currently enrolling patients with high risk ER+ HER2- breast cancer to receive 2 years of palbociclib (PD 0332991) in the adjuvant setting. However, patients who received neoadjuvant PD 0332991 (palbociclib) are not eligible for the adjuvant PALLAS trial. We therefore propose to include in this trial the option of adjuvant PD 0332991 with anastrozole for 23 cycles after chemotherapy and radiation therapy for those who derived benefit from PD 0332991 in the neoadjuvant setting in this trial. This includes:

- The 26 patients who achieved complete cell cycle arrest only after the addition of PD 0332991 (C1D1 Ki67 $>2.7\%$ and C1D15 Ki67 $\leq 2.7\%$) (in the PIK3CA WT, mutant, or unknown cohorts).
- Patients who have a Ki67 $\leq 10\%$ on C1D15 biopsy in the endocrine resistant cohort (including patients enrolled prior to activation of Amendment #7).

All patients (with the exception of those who withdraw consent for follow-up and those who did not undergo surgery) will be followed for invasive disease recurrence and overall survival for 5 years in the adjuvant setting or until recurrence (whichever comes first). Blood will be drawn for serum, plasma, and circulating cell-free DNA (cfDNA) yearly.

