5.7 Treatment/Follow-up Decision Tree

Any patient who registers on study and then withdraws her consent prior to receiving any PD 0332991 will be considered a cancellation. No further follow-up is required. Future treatment is at the discretion of their treating physician.

If a patient is found not to have fulfilled all the eligibility requirements after starting PD 0332991, she will be removed from study treatment. All study forms up to the point of study treatment discontinuation are to be submitted. These patients will be observed for

AEs for 30 days following the last dose of PD 0332991 or the resolution of AEs at least possibly related to PD 0332991, whichever comes later. Future treatment is at the discretion of the treating physician. No further follow-up is required.

All patients except for those who withdrew consent for follow up or who refused to undergo surgery will be followed for 30 days after surgery, then yearly to document recurrence and survival status for 5 years or until recurrence whichever comes first (see Section 10.3).

Patients who received adjuvant PD 0332991 will be followed as described in Section 10.3 during adjuvant PD 0332991 therapy, then yearly following completion of PD 0332991 to complete a total of 5 years of follow-up post surgery. Should a patient discontinue adjuvant PD 0332991 early, she would be followed annually following the completion of PD 0332991 to get as close as possible to 5 years of post-surgery follow-up.

If protocol therapy was discontinued due to Ki67 > 10% on C1D15 or estradiol level in the premenopausal range in patients on goserelin, or discontinued PD 0332991 prior to completion of planned duration of therapy, the patient will be observed for AEs for 30 days following the last dose of PD 0332991 or the resolution of AEs at least possibly related to PD 0332991, then yearly to complete 5 years of follow up after surgery or until recurrence (whichever comes first). Neoadjuvant chemotherapy per physician choice is recommended before surgery. Pathologic response will be documented.

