If there is physical evidence for clinical progression with bi-dimensional tape, ruler, or caliper tumor measurements of the primary tumor, a mammogram and/or ultrasound of the breast should be done to confirm/rule out progressive disease. If there is physical evidence for clinical progression with clinical assessment of the lymph node mass, an ultrasound of the axilla should be done to confirm/rule out progressive disease.

If progression is confirmed by ultrasound **OR** mammographic imaging, discontinue the study drug and operate as soon as possible or begin other anti-neoplastic approaches such as chemotherapy or radiation therapy at the treating physician's discretion. NOTE: Other anti-neoplastic approaches such as chemotherapy or radiation must not be administered while the patient is taking study drug.

For these patients:

- Obtain the serum and plasma samples (can be obtained at surgery)
- Obtain core biopsies (two frozen in OCT and two formalin-fixed) before the patient receives non-protocol chemotherapy (could be obtained at surgery)
- Complete case report form indicating whether the patient will go to immediate surgery or begin other anti-neoplastic approaches such as chemotherapy or radiation therapy. If patient goes to immediate surgery, complete surgery and pathology case report forms.
- Follow-up for 30 days following the last dose of PD 0332991 or the resolution of AEs at least possibly related to PD 0332991, then yearly to complete 5 years of followup after surgery or until recurrence (whichever comes first).

If disease progression is not confirmed by ultrasound or mammographic imaging, study drug may be continued at the investigator's discretion, and the protocol followed as described. These patients are not eligible for adjuvant PD 0332991 therapy.

Clinical progression outside the primary site (i.e., the development of a new breast mass or the development of clinical suspicion for advanced disease) should lead to further imaging evaluation and if confirmed, study drug will be discontinued. Optional tumor biopsy and blood will be obtained prior to the subsequent neoadjuvant therapy or at the time of surgery if surgery is the next step. Subsequent management is at the investigator's discretion. The patient will go off study.

Patients in whom surgery is not performed will be observed for 30-60 days after last dose of study drug and will not undergo annual follow-up.

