10.3 Post Surgery Treatment Calendar

Patients who had a Ki67<10% on the neoadjuvant C1D15 tumor biopsy in the endocrine resistant cohort (before or after activation of Amendment #7) and the 26 patients who enrolled initially to the main trial (PIK3CA WT or mutant cohort) who required PD 0332991 to achieve complete cell cycle arrest have the option of restarting PD 0332991 in combination with anastrozole for adjuvant treatment (23 cycles after surgery). These patients will need to be consented and screened for the adjuvant portion of the study, and may only begin treatment with adjuvant PD 0332991 if they meet the eligibility criteria in Section 3.4 and if they have provided informed consent.

PD 0332991 should be re-started at least 4 weeks after the completion of chemotherapy and radiation therapy if these treatments were planned. Anastrozole may be started earlier while the patient receives radiation therapy if desired. After completion of PD 0332991, patients should continue standard of care hormonal therapy (for example anastrozole) to complete at least 5 years of therapy. Further therapy after that is at the discretion of treating physician.

	Screening	Adjuvant Cycles 1-2		Adjuvant Cycles 3 to 23	End of C23 or early termination	Follow up
Day of cycle	-30 to 0	D1 +/- 3 days	D14 +/- 3 days	D1 +/- 7 days (C3, 6, 9, 12, 15, 18, 21)	4 weeks	+/- 8 weeks
TREATMENT						
Endocrine Therapy ^A		Daily				
PD 0332991		Days 1-21 each cycle				
CLINICAL ASSESSMENT						
Informed consent	X					
Concomitant medication	X	X		X	X	
H&P, PS	X	X		X	X	
Adverse event assessment	X	X	X	X	X	X
ECG	X					
Disease monitoring ^B	X			Per standard of care		
CBC+ differential	X	X	X	X	X	X
Serum chemistry ^C	X	X		X	X	X
Serum/urine pregnancy test ^G	X	X		X	X	
Drug compliance assessment ^D		X		X	X	
Research blood ^E		X		X (C12 only)	X	X

- A. Premenopausal women requires goserelin
- B. Disease monitoring is per standard of care.
- C. Serum chemistry is albumin, alkaline phosphatase, total bilirubin, bicarbonate, BUN, calcium, chloride, creatinine, glucose, potassium, total protein, SGOT/AST, SGPT/ALT, sodium.
- D. Patients will keep a pill diary (Appendix D).
- E. Research blood includes the collection of plasma, serum and whole blood for cfDNA.
- F. For patients who did not receive adjuvant PD 0332991 the follow up is yearly for 5 years post surgery or until recurrence whichever comes first.
- G. In premenopausal women only.

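### The plan disagrees with itself on whether survival follow-up ends at recurrence; if it does, the overall survival analyses in Section 15.5 are informatively censored

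*Combined protocol and SAP*

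**What the plan says.** **Passages that end follow-up at recurrence**

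- Section 1.8, for all women except those who withdraw consent for follow-up or have no surgery: "followed for invasive disease recurrence and overall survival for 5 years in the adjuvant setting or until recurrence (whichever comes first"). Overall survival is named.
- Section 5.7, general paragraph: "then yearly to document recurrence and survival status for 5 years or until recurrence whichever comes first". Survival status is named.
- Postoperative Therapy and Follow-up Schema, women without adjuvant PD 0332991: yearly contact to five years from surgery, ending earlier if the disease recurs.
- The same schema, women given adjuvant PD 0332991: "with follow-up after discontinuation of PD 0332991 taking place annually after the last dose or until recurrence (whichever comes first").
- Section 5.7, women with confirmed progression before surgery: "then yearly to complete 5 years of followup after surgery or until recurrence (whichever comes first").
- Section 10.3, footnote F (covering only women not given adjuvant drug): "For patients who did not receive adjuvant PD 0332991 the follow up is yearly for 5 years post surgery or until recurrence whichever comes first".

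**Passages on the same follow-up with no such stop**

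- Section 5.8, which sets the duration of follow-up: yearly contact on recurrence and survival for five years.
- Section 10.2, footnote C: the same.
- Section 11.0: a Follow-Up Form every year for five years from surgery.
- Section 5.7, paragraph on women given adjuvant PD 0332991: "then yearly following completion of PD 0332991 to complete a total of 5 years of follow-up post surgery". The schema does apply a stop to these women.

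**Analysis.** Section 15.5 describes OS and relapse-free survival (RFS) by Kaplan-Meier and compares them by log-rank test, by complete cell cycle arrest (CCCA) on C1D1, with similar analyses by CCCA on C1D15 and by PEPI 0. It states no censoring rule for OS.

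**The concern.** A site working from Section 5.7 closes a woman's follow-up when she relapses. A site working from Section 11.0 keeps sending a form each year. The OS data set would then depend on which page was read.

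The stop is the more damaging reading. It censors a woman for OS just as her risk of death rises, so the curve labelled OS mainly estimates death without prior recurrence. The censoring is also tied to the groups compared: Sections 1.9.1 and 1.9.6 present on-treatment Ki67 and PEPI as predictors of relapse. OS is therefore overstated most in the group that relapses most, and the comparison is pulled toward no difference.

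A third reading is possible. If footnote F of Section 10.3 is taken with the adjuvant paragraph of Section 5.7, the stop applies only to women without adjuvant drug. In the original cohorts Section 3.5.1 limits that drug to the 26 women with Ki67 above 2.7% on C1D1 and at or below 2.7% on C1D15. All of them fall in the non-arrest group of the C1D1 comparison, so deaths after recurrence could be collected in one compared group and not in the other.

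**Working it through.** The plan gives no OS rate, event count or power, so there is no figure to reproduce. The check sizes the bias with an illness-death model using constant hazards.

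**Inputs from the protocol**
- Five-year RFS of 85% and 60% for the lowest and highest two-week Ki67 groups in IMPACT, with 75% for the middle group (Section 1.9.1).
- As a milder contrast, the crude IMPACT event proportions in Table 2: 13/118 = 11% and 9/35 = 26%, that is RFS 89% v 74%.

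**Assumptions (not in the documents)**
- Death without recurrence: λd = 0.005 to 0.01 per year.
- Median survival after recurrence: m = 1.5 to 5 years, so λp = ln 2 / m.
- RFS either counts death as an event, λr = −ln(RFS)/5 − λd, or counts recurrence only, λr = −ln(RFS)/5.

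**Formulas, with λ = λr + λd**
- True OS(5) = e^(−5λ) + λr·[e^(−5λp) − e^(−5λ)]/(λ − λp).
- Kaplan-Meier OS(5) with censoring at recurrence = e^(−5λd). The recurrence hazard drops out.
- Share of deaths recorded = (λd/λ)·(1 − e^(−5λ)) / (1 − true OS).

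**One case worked through: λd = 0.01, m = 3 (λp = 0.231), death counted in RFS**

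| | RFS 85% | RFS 60% |
|---|---|---|
| λ | 0.0325 | 0.1022 |
| λr | 0.0225 | 0.0922 |
| Alive without recurrence | 0.850 | 0.600 |
| Alive after recurrence | 0.0225 × (0.315 − 0.850)/(0.0325 − 0.231) = 0.061 | 0.0922 × (0.315 − 0.600)/(0.1022 − 0.231) = 0.204 |
| True five-year OS | 0.911 | 0.804 |
| Censored at recurrence | e^(−0.05) = 0.951 | e^(−0.05) = 0.951 |
| Deaths recorded / all deaths | 0.046/0.089 | 0.039/0.196 |
| Deaths missed | 48% | 80% |

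A true gap of 10.7 points becomes zero.

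**Over the whole range of assumptions, RFS 85% v 60%**

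| | RFS 85% | RFS 60% | Gap | Deaths missed |
|---|---|---|---|---|
| True OS | 86–94% | 71–87% | 7–16 points | none |
| Censored as soon as recurrence occurs | 95–98% | 95–98% | 0 | 39–93% |
| Recurrence learned at the next annual contact, earlier deaths captured | 92–97% | 86–95% | 2–6 points | 30–68% |

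The last row comes from simulation. It keeps 27–38% of the true gap.

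**Milder contrast, RFS 89% v 74%, death counted in RFS.** True OS is 91–95% v 82–91%. The estimate is 95–98% in both groups when recurrence is known at once, and 94–97% v 91–96% with annual contact.

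**Stop applied to one group only, identical prognosis (RFS 75%), death counted in RFS.** The group whose follow-up stops reads 95–98%. A group in which everyone continues reads 83–91%, a spurious difference of 5–14 points. If only half of that group continue, the difference is 3–8 points. If RFS counts recurrence only, the first range reaches about 15 points.

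**The case against.** **The conflict is by omission.** Section 5.8, footnote C and Section 11.0 do not mention recurrence, and none says that follow-up continues after it. A general duration can be read subject to the specific stop. That is fair, but it does not rescue the analysis: if the stop governs everywhere, OS is informatively censored under the plan's own rule.

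**The one-group reading is the weakest.** Section 1.8, the general paragraph of Section 5.7 and the schema all extend the stop to women given adjuvant drug. This stands as a caution; the spurious difference is conditional on that reading.

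**The magnitude rests on assumptions.** It does. Mortality before and after recurrence is assumed, and the 85% v 60% contrast is the extreme pair from another trial on endocrine therapy alone, not a CCCA or PEPI 0 split. Knowing of recurrence at once is also an extreme under annual contact. With RFS 89%, deaths missed can be as low as about 27% even with immediate censoring, and recurrence about 6%. The direction needs only that mortality is higher after recurrence than before it.

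**The practical weight is small.** OS is secondary. The C1D15 split reported in Section 1.8 is 39 v 6, so that log-rank test is descriptive under any rule. Even with complete follow-up, 45 women split equally between the 85% and 60% groups would give only about 4 to 9 deaths. All of this stands, and it limits the severity. It does not justify reporting as OS a curve that mainly estimates death without recurrence.

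**Conclusion.** The concern holds. The follow-up passages cannot all be applied as written, and the version that ends survival follow-up at recurrence makes the OS comparisons in Section 15.5 informatively censored. OS would be overstated, more so in the group with more recurrences, and the CCCA and PEPI 0 comparisons attenuated. Under the stated assumptions the loss runs from about two thirds of the true five-year gap (annual contact) to all of it (recurrence known at once). These sizes are illustrative; the direction is not sensitive to them.

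The primary CCCA conclusion and RFS are untouched, and secondary objective 10 on long-term outcomes can still be met through RFS and recurrence. The point should be fixed, but it does not threaten the trial's main result.

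**What to change.** 1. State one rule: vital status is collected yearly to five years after surgery regardless of recurrence, with or without adjuvant PD 0332991. Recurrence assessments and research blood may still end at recurrence.
2. Bring the postoperative schema, Section 1.8, Section 5.7 (all its follow-up paragraphs) and Section 10.3 footnote F into line with Section 5.8, Section 10.2 footnote C and Section 11.0, and say explicitly in each that survival follow-up continues after recurrence.
3. In Section 15.5, state that OS is censored at the date last known alive.
4. If this is not done, delete OS from Section 15.5 and report RFS only.
5. State in the report that women without surgery, who under Section 5.7 "will be observed for 30-60 days after last dose of study drug and will not undergo annual follow-up", are outside the long-term OS follow-up.

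The cost is a small amendment and one vital-status contact or chart check per year, on the existing Follow-Up Form, for each woman who recurs. With 50 women already enrolled in the closed cohorts and up to 37 in the endocrine resistant cohort (50 + 37 = 87), and about 10–40% recurring under the main illustration, that is roughly 5 (0.10 × 50) to 35 (0.40 × 87) women.

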1.9 Correlative Studies Background

1.9.1 Early Tumor Ki67 Assessment during Neoadjuvant Endocrine Therapy to Determine Treatment Response

In this trial, we plan to perform tumor biopsy to assess Ki67 following one month of endocrine therapy (pre-PD 0332991) and 2 weeks on combination of PD 0332991 and anastrozole (Cycle 1 Day 15). This is based on data from previous neoadjuvant endocrine trials which indicated that 2-4 week tumor Ki67 expression on neoadjuvant endocrine therapy is predictive of individual patient outcome long term[11, 25, 26]. In the IMPACT trial, 2-week Ki67 was a significant independent predictor of RFS (HR = 1.95; 95% CI = 1.23–3.07; $P = .004$) [25]. The 5-year RFS rates were 85%, 75%, and 60% for the lowest, middle, and highest values of 2-week Ki67 expression, respectively[25]. In the P024 trial, while baseline Ki67 was not associated with relapse, post 16-week treatment Ki67 levels had a robust association with RFS (HR = 1.4, CI = 1.2–1.6 per natural log unit increase; $P < .001$), and breast cancer-specific survival (HR = 1.4, CI = 1.1–1.7; $P = .009$) [11].

To further investigate these findings, Ellis et al examined the interaction between Ki67 levels and a PAM50-based definition of luminal A breast cancer versus luminal B breast cancer. By using ROC methodology, a cut point of Ki67 10% served as the best surrogate for the LumA versus LumB distinction [99]. The 10%

Ki67 cut point was then applied to the baseline and early on-treatment data in two data sets (Table 2), Preoperative Letrozole study (POL) [13] and IMPACT trial [25]. At baseline the dichotomized Ki67 definition was not significantly predictive for surgical Ki67 level, PEPI score or RFS in these modest sized sample sets. In contrast, high levels of Ki67 on the one month POL samples predicted a higher level of Ki67 in the surgical samples at four months after treatment initiation ($P=.01$), a poorer PEPI score ($P=0.01$), a smaller number of patients in the PEPI-0 group ($P=0.08$) and worse RFS ($P=0.003$). IMPACT data confirmed that a 2-week Ki67 $>10\%$ predicted higher Ki67 in the surgical specimen ($P=0.001$), a poorer PEPI score ($P=0.001$), smaller numbers of patients in the PEPI-0 group ($P= 0.004$) and worse RFS ($P=0.008$) (Table 2.3).

Table 2 Early Ki67 Assessments and Outcome in IMPACT and POL Trials		
POL 4W Ki67	% PEPI 0	RFS (events)
$>10\%$	1/19 (5%)	5/21 (23%)
$\leq 10\%$	10/36 (28%)	1/41 (2.4%)
P Value	$P=0.08$ (Fisher)	$P=0.003$ (log rank)
IMPACT 2W Ki67	% PEPI 0	RFS (events)
$>10\%$	0/32 (0%)	9/35 (26%)
$\leq 10\%$	21/101 (21%)	13/118 (11%)
P Value	$P=0.004$ (Fisher)	$P=0.008$ (log rank)

In this trial, to avoid futile therapy, we plan to obtain tumor biopsy post 2 weeks of PD 0332991 in combination with anastrozole. Patients whose Day 15 Ki67 $>10\%$ will be considered resistant to the combination therapy. These patients will be recommended alternative therapies such as immediate surgery or neoadjuvant chemotherapy. The pre-PD 0332991 Ki67 will not be used for clinical decision making since PD 0332991 will be added to the treatment regimen. It is, however, important to obtain the pre-PD 0332991 Ki67 since this allows a comparison between anastrozole alone and the combination of anastrozole and PD 0332991 on the degree of Ki67 suppression.

1.9.2 To Assess Tumor Cell Apoptosis on Biopsies Taken Pre-PD 0332991 and Cycle 1 Day 15

We will investigate whether there is an increase in tumor cell apoptosis with the combination of PD 0332991 and anastrozole (or anastrozole in combination with goserelin). Anastrozole 1mg daily dosing reduced estradiol level by 70% by 24 hours and by approximately 80% after 14 days of daily dosing [AstraZeneca, Package Insert], therefore, full estrogen deprivation is expected by 28 days of anastrozole administration. In the case of goserelin, serum estradiol is suppressed to levels similar to those observed in postmenopausal women within 3 weeks

following administration. In addition, only 5% or less of women treated with goserelin, FSH and LH may not be suppressed to follicular phase levels on day 28 post treatment with a single 3.6mg depot injection [AstraZeneca, Package Insert].

1.9.3 To Assess the Degree of Ki67 Suppression before (Pre-PD 0332991) and after PD 0332991 (Cycle 1 Day 15)

The degree of Ki67 suppression following 2-4 weeks of therapy has been associated with the effectiveness of endocrine agents or the combination of endocrine agent with an mTOR inhibitor. In the IMPACT trial, suppression of Ki67 after 2 and 12 weeks was significantly greater with anastrozole than with tamoxifen ($P = 0.004$) which mirrored the result based on RFS in the ATAC trial [100]. These data indicate that Ki67 response early on therapy could potentially be employed as a measurement of treatment efficacy.

